#### 4.1.3. Part 3 Study Design

[figure not shown]
Part 3 was initially designed as an open-label study to evaluate safety, reactogenicity, and effectiveness of a 2-dose 50 µg primary series of mRNA-1273.222 SARS-CoV-2 vaccine administered 6 months apart. An interim analysis was conducted which demonstrated robust immunogenicity of a single 50 µg mRNA-1273.222 dose. The pre-specified co-primary endpoints were also achieved allowing inference of vaccine effectiveness of a single dose of mRNA-1273.222 from the pivotal P301 study. Based on these results, in protocol amendment 7 the study design was amended to primarily evaluate the safety, reactogenicity, and effectiveness of a single dose 50 µg primary series of mRNA-1273.222 SARS-CoV-2 vaccine in at least 300 healthy adolescents 12 to <18 years of age.

The study schema and major study events for Part 3 participants who receive Dose 2 is illustrated in [Figure 7](#) and the SoA is described in [Appendix K](#). The study schema and major study events for Part 3 participants who receive a single dose is illustrated in [Figure 8](#) and the SoA is described in [Appendix L](#).

Participants who receive 2 doses of mRNA-1273.222 in Part 3 will be in the study for approximately 7 months including 1 week for Screening (Day -7 to Day -1), 6 months for dosing (Day 1 to Day 181), and 1 month of follow-up after Dose 2.

[figure not shown]
Participants who receive a single dose of mRNA-1273.222 in Part 3 will be in the study for approximately 6 months including 1 week for Screening (Day -7 to Day -1), dosing (Day 1), and 6 months of follow-up after dosing.

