### 3.5.4. Exploratory Endpoints

The exploratory endpoints are the following:

- The GM values of SARS-CoV-2 S2P specific bAb on Day 1, Day 29 (1 month after Dose 1), Day 85 (3 months after Dose 1), and Day 181 (6 months after Dose 1).
- The GM values of SARS-CoV-2-specific nAb on Day 1, Day 29 (1 month after Dose 1), Day 85 (3 months after Dose 1), and Day 181 (6 months after Dose 1).
- The incidence of the first occurrence of symptomatic COVID-19 starting 14 days after Dose 1 of mRNA-1273.222.

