## 6.5. Efficacy Analysis

Analyses of the exploratory efficacy endpoints (incidence rates in COVID-19, SARS-CoV-2 infection, and asymptomatic infection) will be performed using the PP Set for Efficacy and mITT1 Set for long-term and Part 1C-1, and using the FAS for Part 1C-2, Part 2 and Part 3. The PP Set for Efficacy used in blinded phase for mRNA-1273 arm and the mITT1 Set for the long-term analysis will be used for the efficacy analysis in the long term including both the blinded and open label phases; the mITT1 Set for the booster-dose Part 1C-1 will be used for the efficacy analysis in the Part 1C-1 booster dose phase; the FAS will be used for the efficacy analysis in Part 1C-2, Part 2 and Part 3, unless otherwise specified. Subjects will be included in the vaccination group as defined in Section 6.1.

**Baseline SARS-CoV-2 status and Pre-booster SARS-CoV-2 status** is described in [Section 6.1](#). Baseline SARS-CoV-2 status in Part 2 and Part 3, Pre-booster SARS-CoV-2 status in Part 1C-1 and Part 1C-2, the serology test results based on *Roche Elecsys* assay and the RT-PCR test results will be summarized by treatment group.

For mRNA-1273 arm, PP Set for Efficacy and mITT1 set is same as those used in blinded phase. For Placebo-mRNA-1273 cross-over arm, participants with positive or missing SARS-CoV-2 status before the first dose of mRNA-1273 will be excluded from the mITT1 Set for long-term efficacy analysis.

Participants with pre-booster positive or missing SARS-CoV-2 status will be excluded from the mITT1 Set for Part 1C-1 booster dose efficacy analysis.

The serology test results based on Roche Elecsys assay and the RT-PCR test results will be summarized by visit.

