#### 6.5.1.3.Derivation of COVID-19

This is a exploratory efficacy endpoint: the incidence of the first occurrence of COVID-19 starting 14 days after the second dose of IP in long-term (including Part 1B), Part 2 and Part 3, cases counted starting 14 days after the first dose of IP in Part 3, and cases counted starting 14 days after the booster dose of mRNA-1273 in Part 1C-1 and Part 1C-2.

COVID-19 is defined as symptomatic disease based on the criteria specified in [Section 3.2](#). Cases are defined as participants meeting clinical criteria based on both symptoms for COVID-19 and positive RT-PCR test results.

Surveillance for COVID-19 symptoms will be conducted via biweekly telephone calls or eDiary. Subjects reporting COVID-19 symptoms, as defined in [Section 7.3.2 of the protocol](#), will be arranged an illness visit to collect an NP swab.

For this efficacy endpoint, a COVID-19 case will be identified as a positive post-baseline RT-PCR test result, together with eligible symptoms, i.e. a positive PCR result of the eligible symptoms summarized below in Table 2.

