#### **6.5.1.4. Derivation of Secondary Case (CDC Case) Definition of COVID-19**

This is a exploratory efficacy endpoint: the incidence of the first occurrence of COVID-19 cases meeting the secondary case (CDC case) definition, starting 14 days after the second dose of IP in Part 1B, Part 2 and Part 3, starting 14 days after the first dose of IP in Part 3, COVID-19 cases counted starting 14 days after the booster dose of mRNA-1273 in Part 1C-1 and Part 1C-2.

The secondary case definition of COVID-19 is defined by the following criteria:

- One systemic or respiratory symptoms: fever (temperature  $> 38^{\circ}\text{C}/\geq 100.4^{\circ}\text{F}$ ), or chills, cough, shortness of breath or difficulty breathing, fatigue, muscle aches, or body aches, headache, new loss of taste or smell, sore throat, congestion or runny nose, nausea, or vomiting or diarrhea, AND
- At least one positive RT-PCR test for SARS-CoV-2

Date of the documented secondary definition of COVID-19 will be later date of:

- Date of the positive RT-PCR test (prompt by symptom)
- Date of eligible symptom for secondary definition of COVID-19, defined as the earliest date of first eligible symptom is reported

and the two dates should be within 14 days of each other.

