### **6.5.2. Analysis Method**

The number and percentage of subjects who had an event will be summarized in the mITT1 Set for the long-term analysis and Part 1C-1 booster dose phase analysis, and FAS for Part 1C-2, Part 2 and Part 3 analysis.

The incidence rate will be provided by vaccination group if applicable, calculated as the number of cases divided by the total person-time. The 95% CI of the incidence rate will be calculated using the exact method (Poisson distribution) and adjusted by person-time.

Person-time is defined as the total time from date of the 1st dose of each part to the date of event, dose date in next part, last date of study participation, censoring time, or efficacy data cutoff date, whichever is earlier.

Incidence rate will also be analyzed by time period or by calendar month as applicable.

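### Part 3 COVID-19 cases after the second dose are an unlisted count, taken over single-dose participants and over person-time from Dose 1, so the percentage and the rate come out too low

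*SAP*

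**What the plan says.** Section numbers refer to the SAP for Parts 1B, 1C, 2 and 3 unless the Part 1A SAP is named.

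- **Endpoint list.** Section 3.5.4 gives one COVID-19 endpoint for Part 3: "The incidence of the first occurrence of symptomatic COVID-19 starting 14 days after Dose 1 of mRNA-1273.222".
- **COVID-19 derivation.** Section 6.5.1.3 names these starting points, each with a 14-day lag: "second dose of IP in long-term (including Part 1B), Part 2 and Part 3, cases counted starting 14 days after the first dose". The closing clause is also for Part 3, which therefore has two starting points.
- **CDC case derivation.** Section 6.5.1.4 repeats both: "second dose of IP in Part 1B, Part 2 and Part 3, starting 14 days after the first dose of IP in Part 3".
- **Analysis set.** Section 6.5 states that "the FAS will be used for the efficacy analysis in Part 1C-2, Part 2 and Part 3, unless otherwise specified". Section 6.5.2 repeats this for the number and percentage with an event: "and FAS for Part 1C-2, Part 2 and Part 3 analysis".
- **Who is in that set.** Under section 5.1 a single dose qualifies a Part 3 participant for the FAS. Section 6.1 makes Part 3 one vaccination group and takes percentages over the whole group within the analysis set, unless otherwise specified.
- **Person-time.** Section 6.5.2 starts it at the first dose of each part.
- **Design.** Section 4.1.3 of the Part 1A SAP describes two kinds of Part 3 participant. Those given two doses receive the second at Day 181 and are followed for one further month. The others are described as follows: "Participants who receive a single dose of mRNA-1273.222 in Part 3 will be in the study for approximately 6 months".
- **Safety, by contrast.** Section 5.6 defines a Second Injection Safety Set for Part 3, and section 6.3.1 uses it as the denominator for adverse events after the second injection.

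**The concern.** A participant on the single-dose schedule has no second-dose date and can never be a case counted from 14 days after Dose 2. Followed as written, the SAP still keeps that participant in the denominator of the percentage and adds the person's whole follow-up to the denominator of the rate. For two-dose participants the rate also includes the roughly six months before Dose 2 and the first 14 days after it, when no case can count.

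Both figures are then low because of how they are built, not because of what happened after Dose 2. The SAP avoids this for adverse events but has no matching rule for case counts. Because the second-dose count is not in section 3.5.4, it is also unclear whether the table is intended, and one programmer could produce it where another would not. At stake is the meaning of one descriptive table.

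**Working it through.** The SAP gives no figure for this count, so there is nothing to reproduce. The check is what the written rules yield.

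**Inputs**
- Dose 2 at Day 181; end of planned follow-up at Day 209 for two-dose participants (Part 1A SAP, section 4.1.3 and Appendix K) and at Day 181 for single-dose participants (Appendix L).
- First countable day: 181 + 14 = Day 195.
- Countable days per two-dose participant: Days 195 to 209 inclusive, 209 − 195 + 1 = 15.
- f, the share of the Part 3 FAS that receives Dose 2: not in the document. Assumed range 0.10 to 1.
- p, the risk among Dose 2 recipients in the countable window: not in the document. 2% is used for illustration only.

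**Percentage.** FAS percentage = f × p, so the understatement factor is p / (f × p) = 1/f, whatever p is.

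**Incidence rate.** Share of person-time that can hold a countable case = 15f / [209f + 181(1 − f)], taking planned follow-up and ignoring the small loss from events and dropout.

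| f | FAS percentage if p = 2% | 1/f | Share of person-time at risk |
|---|---|---|---|
| 0.10 | 0.2% | 10 | 1.5/183.8 = 0.8% |
| 0.25 | 0.5% | 4 | 3.75/188 = 2.0% |
| 0.50 | 1.0% | 2 | 7.5/195 = 3.8% |
| 0.75 | 1.5% | 1.3 | 11.25/202 = 5.6% |
| 0.90 | 1.8% | 1.1 | 13.5/206.2 = 6.5% |
| 1 | 2.0% | 1 | 15/209 = 7.2% |

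The percentage is right only at f = 1. The rate is not right even there: the reported rate is about 7% of the rate over the days when cases can count, so it is low by a factor of about 209/15 = 13.9.

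**Sensitivity to the length of follow-up.** If the last visit falls at the end of its +7-day window (Day 216), the share at f = 1 is 22/216 = 10.2%. Table 3 in Appendix B still has a Day 361 row for two-dose participants under vital signs and immunogenicity. If follow-up really ran to Day 361, the share would be (361 − 195 + 1)/361 = 167/361 = 46.3%. The rate would still be understated by more than half.

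**The case against.** Several counter-arguments have weight.

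- **The count after Dose 2 is an addition.** Sections 6.5.1.3 and 6.5.1.4 also contain the post-Dose-1 count that section 3.5.4 requires. A reader might infer that the derivations contradict or replace the listed endpoint; they do not. The SAP derives other unlisted counts too, since the CDC case definition is in no Part 3 endpoint list. This stands.
- **Counting these cases is legitimate.** Some Part 3 participants do receive Dose 2, under a schedule that includes COVID-19 surveillance, and the SAP keeps post-Dose-2 safety summaries for them. This also stands. The fault lies in the denominators.
- **Little harm follows.** A reader might infer that a low figure would pass as evidence of high protection after Dose 2. Part 3 is single-arm, and section 6.5.2 plans a number, a percentage and a rate with its confidence interval, with no efficacy estimate, comparator or test. The documents support a risk of misreading, no more.
- **The size is not anchored.** f is not given, so neither a 10-fold nor a 1.3-fold dilution can be claimed, and a near-zero percentage cannot be asserted. This stands for the percentage. The rate result does not depend on f.
- **The window is not uniform in the document.** The Day 361 rows conflict with one month of follow-up after Dose 2. They may be leftovers, and the swab rows of the same table have no Day 361, but the 15-day window holds only on the planned follow-up in section 4.1.3.
- **These are general conventions.** Part 2 also uses an FAS that needs one dose only, and the Part 1A SAP starts person-time at randomization. In Part 1A, however, the rates feed a ratio between arms that share the convention. Part 3 reports a rate alone and contains participants on a single-dose schedule by design. The phrase allowing exceptions leaves room for another denominator, but none is specified.

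**Conclusion.** The point holds in limited form. The SAP derives a Part 3 case count after Dose 2 that its endpoint list does not contain, and the stated rules give figures for it that are too low. The percentage is f times the risk among Dose 2 recipients, with f unknown. The incidence rate is understated even if everyone received Dose 2: on planned follow-up (Dose 2 at Day 181, end at Day 209) about 7% of person-time can hold a countable case, and less at smaller f.

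The effect stops at an exploratory, single-arm, descriptive summary. Both Part 3 coprimary endpoints are antibody levels at Day 29 and cannot be affected, and the listed post-Dose-1 COVID-19 endpoint is fully derived. The correction is worth making because a written rule produces a wrong figure and a few words repair it.

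**What to change.** Either of two changes to the SAP for Parts 1B, 1C, 2 and 3 would do.

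1. Delete Part 3 from the second-dose lists in sections 6.5.1.3 and 6.5.1.4, leaving the post-Dose-1 count of section 3.5.4. This loses the post-Dose-2 summary for participants who are under surveillance.
2. If a post-Dose-2 summary is wanted, list it in section 3.5.4, restrict it to Part 3 participants who received the second injection (as sections 5.6 and 6.3.1 do for safety), and start its person-time 14 days after Dose 2. Restricting the denominator alone would correct the percentage but not the rate.

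The cost is a few words of SAP text and, at most, one table dropped or respecified. No data collection changes.

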**Table 2. Derivation for COVID-19**

	COVID-19
Post-baseline PCR result	Positive, AND
Systemic Symptoms	at least TWO of the following systemic symptoms : Fever ( $\geq 38^{\circ}\text{C}/\geq 100.4^{\circ}\text{F}$ ), chills, myalgia, headache, sore throat, new olfactory and taste disorder(s); OR
Respiratory symptoms	at least ONE of the following respiratory signs/symptoms: cough, shortness of breath or difficulty breathing, OR clinical or radiographical evidence of pneumonia.

The date of documented COVID-19 (case) will be the later date of ([2 systemic symptoms reported, or respiratory symptom reported] and, [date of positive PCR test]). Specifically, the date of documented COVID-19 will be the later date of the following two dates (date of positive PCR test, and the date of eligible symptom(s)), and the two dates should be within 14 days of each other.

- Date of positive PCR test,
- Date of eligible symptom(s), defined as earliest of
  - Respiratory symptom: earliest date of an eligible respiratory symptom is reported
  - Systemic symptoms: earliest date of 2 eligible systemic symptom is reported

#### **6.5.1.4. Derivation of Secondary Case (CDC Case) Definition of COVID-19**

This is a exploratory efficacy endpoint: the incidence of the first occurrence of COVID-19 cases meeting the secondary case (CDC case) definition, starting 14 days after the second dose of IP in Part 1B, Part 2 and Part 3, starting 14 days after the first dose of IP in Part 3, COVID-19 cases counted starting 14 days after the booster dose of mRNA-1273 in Part 1C-1 and Part 1C-2.

The secondary case definition of COVID-19 is defined by the following criteria:

- One systemic or respiratory symptoms: fever (temperature  $> 38^{\circ}\text{C}/\geq 100.4^{\circ}\text{F}$ ), or chills, cough, shortness of breath or difficulty breathing, fatigue, muscle aches, or body aches, headache, new loss of taste or smell, sore throat, congestion or runny nose, nausea, or vomiting or diarrhea, AND
- At least one positive RT-PCR test for SARS-CoV-2

Date of the documented secondary definition of COVID-19 will be later date of:

- Date of the positive RT-PCR test (prompt by symptom)
- Date of eligible symptom for secondary definition of COVID-19, defined as the earliest date of first eligible symptom is reported

and the two dates should be within 14 days of each other.

### **6.5.2. Analysis Method**

The number and percentage of subjects who had an event will be summarized in the mITT1 Set for the long-term analysis and Part 1C-1 booster dose phase analysis, and FAS for Part 1C-2, Part 2 and Part 3 analysis.

The incidence rate will be provided by vaccination group if applicable, calculated as the number of cases divided by the total person-time. The 95% CI of the incidence rate will be calculated using the exact method (Poisson distribution) and adjusted by person-time.

Person-time is defined as the total time from date of the 1st dose of each part to the date of event, dose date in next part, last date of study participation, censoring time, or efficacy data cutoff date, whichever is earlier.

Incidence rate will also be analyzed by time period or by calendar month as applicable.

### **6.5.3. Sensitivity Analysis**

Sensitivity analysis for these efficacy endpoints may be performed with the same methods described above based on the FAS in long-term, or Part 1C-1, and with cases counted starting at different time points as applicable.

## **6.6. Exploratory Analysis**

### **6.6.1. SARS-CoV-2 Exposure and Symptoms**

SARS-CoV-2 reported exposure history and symptoms assessment will be assessed during the study.

SARS-CoV-2 reported exposure history and symptoms assessment will be provided in a listing for each Part separately as applicable.

### **6.6.2. Exploratory Analysis of Efficacy Endpoints**

For the exploratory analysis of efficacy endpoints, in addition to the efficacy endpoint COVID-19 and secondary case (CDC definition) COVID-19 based on eligible symptoms and confirmed positive RT-PCR results (central lab or local diagnostic test) originally defined in SAP, a sensitivity analysis using efficacy endpoint COVID-19 and secondary case (CDC definition) COVID-19 based on both RT-PCR results and other COVID-19 test results including home antigen tests will also be derived. Specifically, each COVID-19 case will be based on eligible symptom(s) and all positive COVID-19 test results including RT-PCR (central lab or local diagnostic test) and (home) antigen test results.

## 6.7. Interim Analysis

More than one IA may be performed.

- The IA of immunogenicity, safety, and efficacy will be performed after Day 57 immunogenicity data are available for the immunogenicity subset and at least 1,500 participants (1,000 participants receiving mRNA-1273) have completed Day 57 (1 month after Dose 2, Part 1A). This IA will be considered the primary analysis of immunogenicity for Part 1A. Details of this IA is described in SAP for Part 1A.
- An IA of immunogenicity and safety may be performed after all or subset of participants who receive BD have completed BD-Day 29 after the BD in Part 1C-1.
- An IA of immunogenicity and safety may be performed after all or subset of participants who receive heterologous BD have completed BD-Day 29 after the BD in Part 1C-2.
- An IA of immunogenicity and safety may be performed after Day 57 immunogenicity data are available after all or a subset of participants in Part 2 have completed Day 57 (1 month after Dose 2, Part 2).
- An IA of immunogenicity and safety may be performed after all or a subset of participants who receive 50 µg mRNA-1273.222 dose have completed Day 29 (1 month after Dose 1).
- At the Sponsor's discretion, a CSR may be developed for the IA.

## 6.8. Final Analysis

The final analysis of all applicable endpoints will be performed after all participants have completed all planned study procedures. Results of this analysis will be presented in a final CSR, including individual listings.

## 8. List of Appendices

### 8.1. Appendix A Standards for Safety and Immunogenicity Variable Display in TFLs

**Continuous Variables:** The precision for continuous variables will be based on the precision of the data itself. The mean and median will be presented to one decimal place more than the original results; the SD will be presented to two decimal places more than the original results; the minimum and maximum will be presented to the same precision as the original results.

**Categorical Variables:** Percentages will be presented to 1 decimal place.

### 8.2. Appendix B Analysis Visit Windows for Safety and Immunogenicity Analysis

Safety and Immunogenicity Analysis will be summarized using the following analysis visit window for post injection assessments:

Step 1: If the safety and immunogenicity assessments are collected at scheduled visit, i.e. nominal scheduled visit, the data collected at scheduled visit will be used.

Step 2: If the safety and immunogenicity assessments are not collected at the scheduled visit, assessments collected at unscheduled visit will be used using the analysis visit windows described in Table 3 below.

If a subject has multiple assessments within the same analysis visit, the following rule will be used:

- If multiple assessments occur within a given analysis visit, the assessment closest to the target study day will be used.
- If there are 2 or more assessments equal distance to the target study day, the last assessment will be used.

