- Per the study protocol, if the visit for the second dose (Day 29) is disrupted and cannot be completed at Day 29 (+7 days) as a result of the COVID-19 pandemic (self-quarantine or disruption of clinical site activities following business continuity plans and/or local government mandates for “stay at home” or “shelter in place”), the window may be extended to Day 29 + 21 days. More rigid visit window may be used in the Per-protocol Immunogenicity Subset as appropriate.

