### **3.4.2. Primary Immunogenicity Endpoints**

The primary immunogenicity objective will be evaluated by the following immunogenicity endpoints:

- GM values of both post Dose 1 (Day 29) and post Dose 2 (Day 57) Ab against ancestral strain in Part 2 of Study P203
- SRR of both post Dose 1 and post Dose 2 from baseline (pre Dose 1) in Part 2 of Study P203 against ancestral strain, using below definition
  - Seroresponse is defined as Ab value change from baseline (pre Dose 1) below the LLOQ to  $\geq 4 \times$  LLOQ, or at least a 4-fold rise if baseline is  $\geq$  LLOQ
  - Seroresponse for sensitivity analysis is defined as Ab value change from baseline (pre Dose 1) below the LLOQ to  $\geq 4 \times$  LLOQ, or at least a 4-fold rise if baseline is  $\geq$  LLOQ and  $< 4 \times$  LLOQ, or at least 2-fold rise if baseline is  $\geq 4 \times$  LLOQ.

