### **Per-protocol (PP) Immunogenicity Subset (Part 2)**

Per-Protocol (PP) Immunogenicity Subset (Part 2) consists of all participants in Immunogenicity Subset (Part 2) who meet all the following criteria:

- a) Received at least one dose of planned injection
- b) Had Day 29 Ab assessment for the analysis endpoint
- c) Had no major protocol deviations that impact key or critical data

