Day 29 (Month 1)	29 (Date of Second Injection)
Day 29 (Month 1)	29 (Date of Second Injection)
Day 57 (Month 2)	57
Day 149 (Month 2)	149 (Date of Booster Dose)
Day 149 (Month 2)	149 (Date of Booster Dose)

Day 177	177	[164, 253]
Day 329	329	[254, 422]
Day 514	514	$\geq 423$
Part 2 (For participants who do not receive booster dose)		
Day 1	1 (Date of First Injection)	$\leq 1$ , Pre-first-dose
Day 1	1 (Date of First Injection)	1, Post-first-dose
Day 29 (Month 1)	29 (Date of Second Injection)	[2, 43] Pre-second-dose
Day 29 (Month 1)	29 (Date of Second Injection)	[2, 43] Post-second-dose
Day 57 (Month 2)	57	[44, 133]
Day 209 (Month 7)	209	[134, 301]
Day 394 (Month 13)	394	$\geq 302$
Part 3 (For participants who receive dose 2)		
Day 1	1 (Date of First Injection)	$\leq 1$ , Pre-first-dose
Day 1	1 (Date of First Injection)	1, Post-first-dose
Day 29 (Month 1)	29	[2, 105]
Day 181 (Month 6)	181 (Date of Second Injection)	[106, 195] Pre-second-dose
Day 181 (Month 6)	181 (Date of Second Injection)	[106, 195] Post-second-dose
Day 209 (Month 7)	209	[196, 285]
Day 361 (Month 12)	361	$\geq 286$
Part 3 (For participants who receive a single dose)		
Day 1	1 (Date of First Injection)	$\leq 1$ , Pre-first-dose
Day 1	1 (Date of First Injection)	1, Post-first-dose
Day 29 (Month 1)	29	[2, 105]
Day 181 (Month 6)	181	$\geq 106$
Immunogenicity		
Part 1B, Part 1C-1 and Part 1C-2		
OL-Day 1	1 (Date of First Injection in Part 1B) relative to OL-Day 1	1, Pre-first-dose

OL-Day 57 (Month 2)	57 relative to OL-Day 1	≥44 and before BD-Day 1 for subject receiving BD
OL-Day 57 (Month 2)	57 relative to OL-Day 1	[44, 117] for subject declining BD
OL-Day 178 (Month 6)	178 relative to OL-Day 1	≥18 for subject declining BD
BD-Day 1	1 (Date of Injection in Part 1C-1, Part 1C-2) relative to BD-Day 1	≤1 and V[SIT is BD-Day 1
BD-Day 29 (Month 1)	29 relative to BD-Day 1	[2, 105]
BD-Day 181 (Month 6)	181 relative to BD-Day 1	[106, 271]
BD-Day 361 (Month 12)	361 relative to BD-Day 1	>272
Part 2 (For participants who receive booster dose)		
Day 1	1 (Date of First Injection)	1, Pre-first-dose
Day 29 (Month 1)	29 (Date of Second Injection)	[2, 43]
Day 57 (Month 2)	57	[44, 103]
Day 149 (Month 2)	149 (Date of Booster Dose)	[104, 163]
Day 177	177	[164, 253]
Day 329	329	[254, 422]
Day 514	514	≥423
Part 2 (For participants who do not receive booster dose)		
Day 1	1 (Date of First Injection)	1, Pre-first-dose
Day 29 (Month 1)	29 (Date of Second Injection)	[2, 43]

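### Part 2 post-dose-2 antibody results are taken from a per-protocol set that does not require dose 2, and several fallback antibody windows cross a dosing day or run far beyond the planned visit

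*SAP*

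**What the plan says.** **Part 2 endpoints and population (Part 1B/1C/2/3 SAP).** Section 3.4.2 sets the primary endpoints as "GM values of both post Dose 1 (Day 29) and post Dose 2 (Day 57) Ab against ancestral strain", with SRRs at the same two visits. Section 5.3 defines the Part 2 per-protocol (PP) immunogenicity subset by three criteria: "Received at least one dose of planned injection", a Day 29 antibody result, and no major deviation affecting key data. Sections 5.3 and 6.4 make its baseline-positive subset the main Part 2 immunogenicity population. Section 6.4.3 reports the Day 57 GM and SRR and compares them descriptively with Study P301. It names a set only for the Day 29 comparison.

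**Windowing rule.** In Appendix B (Section 8.2; the Part 1A SAP has the same rule in Section 9.2), Step 1 says that if a nominal-visit sample exists, "the data collected at scheduled visit will be used". Step 2 says that otherwise "assessments collected at unscheduled visit will be used using the analysis visit windows described in Table 3 below". Among several samples the closest to target is chosen, and "If there are 2 or more assessments equal distance to the target study day, the last assessment will be used".

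**Antibody windows, in study days.**
- Part 2 Day 29: [2, 43]
- Part 2 Day 149 (booster day): [104, 163]
- Part 3 Day 181 (second-dose day): [134, 195]
- BD-Day 29, counted from the booster: [2, 105]
- Part 1A Day 57 (Part 1A SAP, Table 6): [44, 133]

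**Second-dose timing.** For pandemic disruption, Section 6.4.4 of the Part 1A SAP says "the window may be extended to Day 29 + 21 days".

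**The concern.** A value labelled post-dose-2 should come from someone who has had two doses, and a value labelled for a dosing-day visit should precede that day's dose. The Part 2 PP set does not secure the first, even when every sample is taken at its nominal visit. The fallback windows do not secure the second, because they are set by study day alone.

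The Part 2 Day 57 GM and SRR could therefore mix one-dose and two-dose responses. Part 2 Day 29 could include responses to dose 2, and the Part 3 Day 181 persistence values could include responses to the second dose. For Part 1A Day 57 and BD-Day 29, which feed formal coprimary tests, a fallback sample could be taken far from 28 days after the last dose. In Part 1A it could even precede a delayed second dose.

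**Working it through.** **1. Part 2 set against the other parts.**
- Part 1A (Part 1A SAP, 5.4): planned doses per schedule, dose-2 timing, and a Day 57 result.
- Part 1C-1 (5.3): two doses in Part 1A per schedule, the booster, and a BD-Day 29 result.
- Part 3 (5.3): planned doses per schedule and a Day 29 result.
- Part 2 (5.3): at least one dose and a Day 29 result. Neither dose 2 nor a Day 57 result is required.

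Section 6.2.1 plans to tabulate Part 2 participants who stop before the second dose, so such participants are foreseen. One who still gives a nominal Day 57 sample meets every stated criterion unless the major-deviation rules exclude them. Section 6.2.6 leaves those rules to be finalised before database lock.

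**2. Reproducing the window limits.** Each upper limit is the midpoint between adjacent target days, and all match the tables.
- (29+57)/2 = 43
- (149+177)/2 = 163
- (181+209)/2 = 195
- (29+181)/2 = 105 (booster scale)
- (57+209)/2 = 133

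Midpoints take no account of doses.

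**3. Days on the wrong side of a dose.** Days after a dose on day d in a window ending on day U are U − d.
- Part 2 Day 29: length 43 − 2 + 1 = 42. Dose on Day 29: 43 − 29 = 14 days after it. Dose on Day 36 (29+7): 7 days. With dose 2 on Day 29, samples on Days 28 and 30 are equally distant, and the tie rule picks Day 30, which is after dose 2.
- Part 2 Day 149: length 163 − 104 + 1 = 60. Booster on Day 149: 14 days after it. Booster at the earliest allowed Day 121 (149 − 28): 42 days.
- Part 3 Day 181: length 195 − 134 + 1 = 62. Dose on Day 181: 14 days after it.
- Part 1A Day 57: latest dose 2 is Day 29 + 21 = Day 50, so Days 44 to 49 (6 days) can precede it.

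**4. Timing only.**
- BD-Day 29: samples 1 to 104 days after the booster qualify, which is 104 study days. The planned allowance of −3/+14 (Part 1A SAP, Appendix G) gives study days 26 to 43, which is 18 days.
- Part 1A Day 57: the latest sample is 133 − 29 = 104 days after a Day 29 second dose.

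**5. Illustrations. All inputs are assumed; the documents give none.**
- If a fraction f of the set lacks dose 2 and has a GM k times lower, the Day 57 GM is multiplied by k^(−f). With f = 5%, k = 2: 0.97. With f = 20%, k = 5: 0.72. With k = 1 nothing changes.
- With a titer half-life of 50 to 100 days, a sample at 104 rather than 28 days reads 2^(−76/50) = 0.35 to 2^(−76/100) = 0.59 of its 28-day value. If 3 of 289 values were affected at 0.35, the GM factor is 0.35^(3/289) = 0.99. At 5% of values it is 0.35^0.05 = 0.95.

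**The case against.** Much of the case on the other side stands.

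- **The windows are a fallback.** They act only when the nominal sample is missing and an unscheduled one exists. Scheduled dosing-day blood must be drawn before the dose. The vital-sign rows for Part 2 without booster and Part 3 with dose 2 separate pre-dose from post-dose values, but vital signs are measured on both sides of the dose. The contrast with the antibody rows is therefore weak evidence of an oversight.
- **Dose-count errors fall mainly where nothing is tested.** Section 4.2.2 makes Part 2 descriptive, and Part 3 Day 181 is exploratory. The Part 1A case needs a delayed dose, a missed nominal visit and an early unscheduled sample together, and the PP set already requires compliance with dose-2 timing.
- **The Part 2 endpoint label itself says post Dose 2.** A programmer might apply that restriction unprompted, but the analysis set does not state it.
- **The Part 1A SAP (6.4.4) lets a tighter window be used in the PP subset.** This is optional, unquantified and confined to that SAP.

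A reader might infer three stronger things, none of which the documents support.

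- That BD-Day 29 values can reflect the wrong number of doses. The window is anchored on the booster, no scheduled dose falls inside it, and the PP set requires two doses plus the booster. Only timing is at risk.
- That convalescent blood can stand in for BD-Day 29. Appendix G lists no convalescent draw. Such draws appear in Appendix E (Part 1A) and Appendix I (Part 2 with booster).
- That the reported coprimary results are biased towards success. No affected count is available, and waned or one-dose adolescent values would lower the geometric mean ratio, which works against noninferiority.

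**Conclusion.** The Part 2 point holds on the text and needs no missing sample: the primary Day 57 summaries rest on a set that admits one-dose participants. It should be corrected, though Part 2 is descriptive and Section 4.3.3 expects it to be small. A small set also means that a few such participants could move the GM.

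The window point holds as a secondary gap in the fallback rule. Wrong dose count is possible for Part 2 Days 29 and 149, Part 3 Day 181 and, rarely, Part 1A Day 57. Wrong timing is possible for BD-Day 29 and Part 1A Day 57.

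How often either occurs, and how far it shifts a GM or SRR, cannot be computed from the document. The factors 0.97 to 0.72 and 0.35 to 0.59 rest wholly on assumed inputs. For the coprimary endpoints the effect is probably small.

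**What to change.** 1. For all Part 2 Day 57 summaries, restrict the PP subset and its baseline-positive subset to participants who received dose 2 per schedule and have a Day 57 result.
2. Add a pre-dose limit to the antibody rows for Part 2 Day 29, Part 2 Day 149 and Part 3 Day 181.
3. Require any Day 57 sample to follow dose 2. In the PP sets, limit Day 57 and BD-Day 29 fallback samples to a range tied to the planned visit allowance, counted from the actual last dose.
4. Exclude convalescent samples from these windows where the schedule draws them (Part 1A and the Part 2 booster schedule).
5. Do not re-window the Part 1A and Part 1C-1 coprimary tests, which Section 4.4 reports as completed on data of 08 May 2021 and 16 May 2022. Apply the tighter windows there as a sensitivity analysis and report how many values change.

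The cost is SAP wording, windowing code and the loss of a few evaluable values. No new data are needed.
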